## 1.2 Purpose

The purpose of this study is to assess the efficacy of secukinumab at Week 12, based on both PASI 75 and IGA mod 2011 0 or 1 response rates in children and adolescents aged 6 to less than 18 years at randomization with moderate to severe chronic plaque psoriasis who are candidates for systemic therapy.

This study will provide efficacy, safety and pharmacokinetic data to support the extension of label of secukinumab to include children and adolescents (6 years to <18 years) with moderate to severe chronic plaque psoriasis.

Moreover, this study will assess the long-term efficacy, safety and tolerability of secukinumab over a period of up to 4 years to support the long-term use of secukinumab in pediatric patients.

## 2 Study objectives and endpoints

### 2.1 Objectives and related endpoints

**Table 2-1 Objectives and related endpoints**

Objective(s)	Endpoint(s)
Primary Objective(s)	Endpoint(s) for primary objective(s)
To evaluate the efficacy of secukinumab in pediatric subjects aged 6 years to less than 18 years old with moderate to severe chronic plaque psoriasis with respect to PASI 75 and IGA mod 2011 0 or 1 response (co-primary endpoints) at Week 12, compared to placebo (historical control).	Proportion of subjects who achieved PASI 75 and IGA mod 2011 0 or 1 response at Week 12 in each secukinumab treatment group (low dose and high dose). Placebo data are obtained from adult secukinumab placebo-controlled trials and pediatric placebo-controlled trials with secukinumab or other biologics
Secondary Objective(s)	Endpoint(s) for secondary objective(s)
To evaluate the efficacy of secukinumab in pediatric subjects with respect to PASI 90 at Week 12, compared to placebo (historical control).	Proportion of subjects who achieved PASI 90 response at Week 12 in each secukinumab treatment group (low dose and high dose). Placebo data are obtained from adult placebo-controlled trials and pediatric placebo-controlled trials
To investigate the clinical safety and tolerability of secukinumab as assessed by growth, weight gain, vital signs, clinical laboratory variables, ECGs, and adverse event monitoring	Height and weight, vital signs, laboratory evaluations, ECG and adverse events
To evaluate the pharmacokinetics of secukinumab in pediatric subjects	Secukinumab concentration in serum at various time points
Exploratory Objective(s)	Endpoint(s) for exploratory objective(s)
To investigate the effects of treatment with secukinumab with respect to changes in CDLQI over time up to End of Treatment	Absolute and percentage change from baseline of CDLQI score over time up to End of Treatment
To investigate the effects of treatment with secukinumab with respect to CDLQI 0 or 1 score over time, up to End of Treatment	Proportion of subjects achieving CDLQI 0 or 1 over time up to End of Treatment

[figure not shown]
Exploratory Objective(s)	Endpoint(s) for exploratory objective(s)
To investigate the development of immunogenicity against secukinumab	Development of anti-Drug Antibodies (ADA) to secukinumab

### 3 Investigational plan

#### 3.1 Study design

This is an open-label, parallel-group, two-arm, multi-center, trial in pediatric subjects aged 6 years to less than 18 years, at randomization, with moderate to severe chronic, plaque psoriasis. Approximately 80 subjects (at least 60 subjects with moderate severity) will be enrolled. It is expected that subjects will be enrolled in about 40 centers worldwide. It will be targeted to have at least 5 subjects in the < 25kg weight, and at least 10 subjects in each of the other two weight groups.

**Figure 3-1** Study design

The study consists of 3 periods: screening (up to 4 weeks), treatment (of 208 weeks) and post-treatment follow-up (of 16 weeks). An outline of the visits is presented in [Figure 3-1](#) while a detailed visit and assessment schedule can be found in [Table 6-1](#), [Table 6-2](#).

## Screening Period

The screening period of up to 4 weeks will be used to assess eligibility of the subjects and to taper subjects off prohibited medication.

## Treatment Period

The treatment period is defined as randomization to Week 208. In this period the endpoints are assessed and subjects are followed for long-term safety and efficacy. Subjects will be randomized using 1:1 ratio into either secukinumab low dose or secukinumab high dose. Randomization will be stratified by body weight (< 25kg, 25-< 50 kg,  $\geq$  50kg) and disease severity (either moderate (PASI score 12-<20 and IGA 3 or 4 or PASI score  $\geq$  20 and IGA 3) or severe (PASI score  $\geq$  20 and IGA of 4), collected at Randomization Visit. The study aims to recruit at least 60 subjects with moderate disease severity and approximately 20 subjects with severe disease severity. It will be targeted to have at least 5 subjects in the < 25kg weight, and at least 10 subjects in each of the other two weight groups. Subjects will receive the appropriate dose based on their body weight category. If a subject moves into a higher or lower weight group at two consecutive visits with weight measurements during the maintenance (from Week 12 onwards as assessed at 4 weekly visits or during extension treatment period (as assessed at scheduled site visits), the subject will receive dosing according to the new (higher or lower) weight group respectively. The dose will be adapted starting from the visit of the second consecutive weight change.

Adolescents (12-< 18 years) and children (6-< 12 years) can be included from the beginning of this study, since the DMC has approved already the enrollment of children (6-< 12 years) in study CAIN457A2310.

All subjects will visit the study site at Randomization (Day 1) and at Weeks 1, 2, 3, 4, 8, 12, 16 during which they will receive either high-dose or low-dose secukinumab treatment subcutaneously. Additionally, subjects will visit the site at Weeks 13, 14, 15 to provide blood samples for pharmacokinetics.

During the Treatment period subjects will receive treatment of the assigned secukinumab dose every 4 weeks. However during Weeks 16-52 site visits will be scheduled every 8 weeks and from Weeks 64-208 site visits will be scheduled every 12 or 16 weeks, to minimize the burden on the subject. Subjects will have the option to receive treatment between scheduled visits at home, following instructions provided to the subject (if  $\geq$ 12 years old), parent or caregiver.

Subjects who discontinue study treatment for any reason before the end of the Treatment Period (Week 208) should have the Week 208 visit assessments performed approximately 4 weeks after their last dose of secukinumab. The subject will then enter the treatment-free Follow-up Period.

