### 5.6 Study completion and discontinuation

#### 5.6.1 Study completion and post-study treatment

A subject will be considered to have completed the study when the subject has completed the Week 224 visit as per the protocol. For subjects who discontinue prior to this, the study completion corresponds to the last study visit of the subject or contact of the site with custodian/subject. Study completion for the study will occur when all randomized subjects have completed the study as stated above.

The investigator must provide follow-up medical care for all subjects who are prematurely withdrawn from the study, or must refer them for appropriate ongoing care.

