### 5.6.2 Discontinuation of study treatment

Discontinuation of study treatment for a subject occurs when study drug is stopped earlier than the protocol planned duration, and can be initiated by either the subject/custodian or the investigator.

The investigator must discontinue study treatment for a given subject if, on balance, he/she believes that continuation would negatively impact the risk/benefit of trial participation.

Study treatment must be discontinued under the following circumstances:

- Subject/custodian's wish
- Withdrawal of consent
- Pregnancy (see [Section 6.5.8](#) and [Section 7.6](#))
- Ongoing use of prohibited treatment as per recommendations in [Table 5-3](#)
- Emergence of the following AEs: AEs that in the judgment of the investigator/qualified site staff, taking into account the subject's overall status, prevent the subject from continuing study treatment, for example sepsis, or newly occurring or worsening Inflammatory Bowel Disease, including Crohn's disease and ulcerative colitis.
- Any laboratory abnormalities that in the judgment of the investigator/qualified site staff, and taking into consideration the subject's overall status, prevents the subject from continuing study treatment.
- Live vaccination
- Any situation where study participation results in a significant risk to subject's safety

If discontinuation of study treatment occurs, the subject should NOT be considered withdrawn from the study. If the subject discontinued study treatment within the treatment period, the subject should return to the clinic after discontinuation of study drug, for Week 208 and Follow-up visits (Week 212, Week 216 and Week 224).

At the time of the study treatment discontinuation visit, if it has been approximately 4 weeks post last dose of study treatment then the assessments described at Week 208 visit in [Table 6-2](#) should be completed and recorded in the eCRF.

If it has not been approximately 4 weeks post last dose of study treatment at the time of the study treatment discontinuation visit, then the subject should be scheduled to return 4 weeks post last dose for their Week 208 visit.

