**Table 6-2      Assessment schedule - Years 2-4 (continued)**

Period	Treatment Period (years 2-4)												Follow-up Period b			Unscheduled d
Week	64	76	88	104	116	128	140	156	168	180	192	208 EOT	212	216	224 EOF	
Day	449	533	617	729	813	897	981	1093	1177	1261	1345	1457	1681	1709	1765	
Concomitant medications 	Update as necessary															x
Surgeries and non-drug procedures	Update as necessary															x
Physical Exam	S	S	S	S	S	S	S	S	S	S	S	S	s		S	S
Height 	x	x	x	x	x	x	x	x	x	x	x	x	x	x	x	x
Weight	x	x	x	x	x	x	x	x	x	x	x	x	x	x	x	x
Vital signs (BP & pulse)	x	x	x	x	x	x	x	x	x	x	x	x	x	x	x	x
Hematology 	x	x	x	x	x	x	x	x	x	x	x	x	x	x	x	x
Blood Chemistry  , Urinalysis (local)	x	x	x	x	x	x	x	x	x	x	x	x	x	x	x	x
Urine Pregnancy test (local; in females of childbearing potential) 	S	S	S	S	S	S	S	S	S	S	S	S			S	S
ECG (standard 12-lead)				x		x		x		x		x			x	x
Blood sample for IG 				x				x				x			x	x 
Blood sample for PK 				x				x				x			x	x 
PASI	x	x	x	x	x	x	x	x	x	x	x	x	x	x	x	x
IGA mod 2011	x	x	x	x	x	x	x	x	x	x	x	x	x	x	x	x
CDLQI 	x	x	x	x	x	x	x	x	x	x	x	x				x

Period	Treatment Period (years 2-4)												Follow-up Period b			Unscheduled d
	64	76	88	104	116	128	140	156	168	180	192	208 EOT	212	216	224 EOF	
Week	64	76	88	104	116	128	140	156	168	180	192	208 EOT	212	216	224 EOF	
Day	449	533	617	729	813	897	981	1093	1177	1261	1345	1457	1681	1709	1765	
(Serious) Adverse event assessment	Update as necessary															x
Data entry of weight into IRT 	x	x	x	x	x	x	x	x	x	x	x	x				
Contact IRT	x	x	x	x	x	x	x	x	x	x	x	x				
Administration of Study Drug 	x	x	x	x	x	x	x	x	x	x	x					
End of Treatment												x				
Study completion															x	

R=randomization, PK=pharmacokinetics, ECG=Electrocardiogram, CDLQI= children's dermatology life quality index, IRT=Interactive response technology,

X=assessment entered or transferred into the clinical database. S= assessment only recorded in source

aDuring EOT visit, subjects will have their last assessments performed for treatment period. This visit will also be performed for all subjects who will discontinue early the treatment period.

bFollow-up assessments are to be conducted for subjects who complete treatment period and for subjects who discontinue study treatment early

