## 14 Appendix 2: Blood collection log for pharmacokinetics and immunogenicity

**Table 14-1 Blood collection log for pharmacokinetics**

Visit	Timepoint	Volume	Analyte	Sample number 	PK collection number /Dose Reference ID 
Randomization/Day 1	Pre-dose	1 mL	AIN457 for PK	1	1
Week 4	Pre-dose	1 mL	AIN457 for PK	2	2
Week 12	Pre-dose	1 mL	AIN457 for PK	3	3
Week 13	168 hours 	1 mL	AIN457 for PK	4	3
Week 14	336 hours 	1 mL	AIN457 for PK	5	3
Week 15	504 hours 	1 mL	AIN457 for PK	6	3
Week 16	672 hours 	1 mL	AIN457 for PK	7	3
Week 24	Pre-dose	1 mL	AIN457 for PK	8	4
Week 52	Pre-dose	1 mL	AIN457 for PK	9	5
Week 104	Pre-dose	1 mL	AIN457 for PK	10	6
Week 156	Pre-dose	1 mL	AIN457 for PK	11	7
Week 208	672 hours 	1 mL	AIN457 for PK	12	8
Week 224	3360 hours 	1 mL	AIN457 for PK	13	8

 If a PK sample is collected at an unscheduled visit, the sample numbers will follow the pattern: 1001, 1002, etc.

 Scheduled time points for sample numbers 4, 5, 6, 7 (168, 336, 504 and 672 hours post-dose, respectively) refer to the last previous dose given at Week 12 (Dose Reference ID = 3)

 Scheduled time points for sample numbers 12 and 13 (672 and 3360 hours post-dose, respectively) refer to the last dose given at Week 204 (Dose Reference ID = 8)

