2.4.1.1 Visit window

Visit-windows will be applied to data summarized by visit. These will be based on study evaluation schedule and comprise a set of days around the nominal visit day. For any assessment, there are the protocol defined scheduled visits around which visit windows are created to cover the complete range of days within the study. The visit windows are shown in

Table 2-3. In this table, the days are counted since the first dose of study treatment (study days) for safety assessments, and the days are counted since the date of randomization for efficacy assessments. These visit windows apply to measurements taken at every visit. For assessments collected less often different visit windows will be applied as detailed below.

When visit windows are used, all visits will be re-aligned, i.e., they will be mapped into one of the visit windows. E.g., if the *Week 4* visit of a subject is delayed and occurs on Day 60 instead of on Day 29, it will be re-aligned to visit window *Week 12*. In the case of major deviations from the visit schedule, or due to unscheduled visits, several assessments of a subject may fall in a particular visit window (either scheduled or unscheduled). Statistical approaches to handle multiple assessments in a given visit window are specified below.

The analysis visit will be used for listing of visit and period for safety data. If a visit falls after the last visit window, it is not assigned an analysis visit and will be listed under label “After Week xxx”.

Table 2-3 Assessment windows for scheduled visits

Analysis Visit	Week	Scheduled Day	Visit Window
Baseline	BSL	1	-28 days to Day 1*
Week 1	1	8	Day 2-11
Week 2	2	15	Day 12-18
Week 3	3	22	Day 19-25
Week 4	4	29	Day 26-43
Week 8	8	57	Day 44-71
Week 12	12	85	Day 72-99
Week 16	16	113	Day 100-141
Week 24	24	169	Day 142-197
Week 32	32	225	Day 198-253
Week 40	40	281	Day 254-309
Week 48	48	337	Day 310-351
Week 52	52	365	Day 352-407
Week 64	64	449	Day 408-491
Week 76	76	533	Day 492-575
Week 88	88	617	Day 576-673
Week 104	104	729	Day 674-771
Week 116	116	813	Day 772-855
Week 128	128	897	Day 856-939
Week 140	140	981	Day 940-1037
Week 156	156	1093	Day 1038-1135
Week 168	168	1177	Day 1136-1219
Week 180	180	1261	Day 1220-1303
Week 192	192	1345	Day 1304-1401
Week 208 (EOT)	208	1457	Day 1402-1471

Week 212	212	1485	Day 1472-1499
Week 216	216	1513	Day 1500-1541
Week 224 (EOF)	224	1569	Day 1542-1597

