2.9 Pharmacokinetic endpoints

All completed subjects with quantifiable pharmacokinetic (PK) measurements of secukinumab will be included in the pharmacokinetic data analysis.

Serum concentrations will be expressed in mass per volume units. All concentrations below the limit of quantification (BLQ) as well as missing data will be labeled as such in the concentration data listings. BLQ concentrations will be included in the summaries. Serum concentration data from patients who missed a dose or doses will be excluded at the following visit(s).

PK concentrations will be summarized by eCRF visit and treatment. PK concentrations will also be presented by visit (i.e., CRF visit), dose group (75 mg, 150 mg, 300 mg) and body weight categories at visit (<25 kg, 25 to <50kg, \geq 50 kg). Per protocol, a subject will change into a higher or lower weight category and dose, when the subject's weight moves into a different weight category for two consecutive visits. This change is assessed from Week 12, then at week 16 and bimonthly until week 52 and at trimonthly visits in the extension phase. If such a change happens, in the PK summaries, at the concerned assessment points, the subject will be accounted in the new dose group (75 mg, 150 mg, 300 mg) and weight category group.

In addition to mean, standard deviation (SD), coefficient of variation (CV), median and quartiles, the geometric mean and geometric coefficient of variation (CV) and n(log) will be presented. The formula for deriving the geometric mean and CV (%) is as following:

- $CV\% = (SD/\text{mean}) * 100$,
- geometric mean = $\exp(\text{sum of log transformed data}) / \text{number of non-missing data points after log transformation}$,
- geometric CV = $\sqrt{\exp(\text{variance of log-transformed data}) - 1} * 100$.

In addition, sample number, concentration, sample date, elapse time since day of first secukinumab dose, reason excluding from analysis will be listed by treatment.

[figure not shown]
Values below lower limit of quantification/below detection limit will be imputed by 0.

Pharmacokinetic derived parameters AUC84-112d, Tmax and Cmax will be summarized by treatment group (AIN457 low dose and AIN457 high dose). Descriptive summary statistics include mean (arithmetic and geometric), SD, and CV (arithmetic and geometric), median, minimum and maximum. Derived pharmacokinetic parameters will be listed by treatment sequence.

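### The Week 208 and Week 224 PK rows would pool samples that follow the Week 204 dose with samples from early stoppers taken months to years earlier

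*Protocol*

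**What the plan says.** **Early stoppers.** Protocol 3.1 (Treatment Period) says that anyone stopping before Week 208 "should have the Week 208 visit assessments performed approximately 4 weeks after their last dose of secukinumab". Protocol 5.6.2 agrees: if the stopping visit comes sooner than about 4 weeks after the last dose, "then the subject should be scheduled to return 4 weeks post last dose for their Week 208 visit". Footnote a to Table 6-2 says of the EOT visit: "This visit will also be performed for all subjects who will discontinue early the treatment period". The row "Blood sample for PK" in that table is marked at Weeks 104, 156, 208 and 224. Early stoppers are also expected at the follow-up visits, including Week 224.

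**Nominal sample times.** Protocol Table 14-1 puts the Week 208 and Week 224 samples at 672 and 3360 hours. Footnote 3 says that these times "refer to the last dose given at Week 204". There is no variant for early stops.

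**Tabulation.** SAP 2.4.1.1 assigns by-visit data by study day; all visits are re-aligned, so that "they will be mapped into one of the visit windows". SAP 2.9 departs from this: "PK concentrations will be summarized by eCRF visit and treatment". A second PK summary is by CRF visit, dose group and weight category. Section 2.9 reads the same on these points in the 2020 and 2023 SAPs.

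**Filters.** SAP 2.9 covers completed subjects with quantifiable measurements, and drops concentrations at visits that follow missed doses. It does not define completed. Protocol 5.6.1 does, for the study: "A subject will be considered to have completed the study when the subject has completed the Week 224 visit as per the protocol".

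**The concern.** Serum concentration over time is a secondary endpoint (Protocol Table 2-1, SAP Table 1-2). Doses are set by weight band in growing children so that exposure stays comparable across weights (Protocol 3.6). Week 208 is the only on-treatment PK row at four years, and a reader will take it as trough exposure after four years of treatment and growth. If early stoppers carry the same visit label, the row's n overstates how many subjects reached that time, and its summary statistics mix ages, weights and dose bands. For very early stops it may also include residual drug from the weekly doses of the first month. The Week 224 row, meant to describe concentrations 20 weeks after the Week 204 dose, has the same problem.

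**Working it through.** **1. The plan's own figures.** Table 14-1 reproduces for subjects who complete treatment: (208 − 204) × 168 h = 672 h and (224 − 204) × 168 h = 3360 h. Study day = 7 × week + 1, so Week 208 is Day 1457, as in SAP Table 2-3.

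**2. Early stoppers.** For a last dose at week *w*, the sample labelled Week 208 falls at week *w* + 4, which is (204 − *w*) weeks before the nominal visit.

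| Last dose (week) | Sample week | Study day | Days before Day 1457 | Years | SAP Table 2-3 window by study day |
|---|---|---|---|---|---|
| 12 | 16 | 113 | 1344 | 3.7 | Week 16 (100–141) |
| 48 | 52 | 365 | 1092 | 3.0 | Week 52 (352–407) |
| 100 | 104 | 729 | 728 | 2.0 | Week 104 (674–771) |
| 152 | 156 | 1093 | 364 | 1.0 | Week 156 (1038–1135) |
| 176 | 180 | 1261 | 196 | 0.5 | Week 180 (1220–1303) |
| 196 | 200 | 1401 | 56 | 0.15 | Week 192 (1304–1401) |
| 200 | 204 | 1429 | 28 | 0.08 | Week 208 (1402–1471) |

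Only the last line falls in the Week 208 window. For a subject last dosed at Week 48, the same EOT visit would count as Week 52 for PASI and as Week 208 for PK.

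**3. Week 224.** With the planned follow-up spacing, this sample falls at week *w* + 20, so it is early by the same (204 − *w*) weeks. Mapping it by study day would not help. For a last dose at Week 48 it falls at Week 68, Day 7 × 68 + 1 = 477. PK is not sampled at Weeks 64, 76 or 88, so SAP 2.4.1.1 would merge those windows with Week 104 (Day 408–771). A sample 20 weeks off drug would then sit in the on-treatment Week 104 row.

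**4. Do the filters remove these samples?** The missed-dose rule does not reach a sample taken when the next 4-weekly dose would have been due. Under Protocol 5.6.1 completion means attending Week 224, and early stoppers are asked to attend it.

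**5. How many samples, and which direction?** The documents give no dropout rate. Assuming 10–30% of 40 subjects per arm stop early and attend, 4 to 12 samples per arm would be affected. Assuming also that trough is proportional to mg/kg, the direction depends on the weights chosen:
- Same dose, 32–36 kg at the early sample against 45 kg at Week 208: the early sample is 45/36 = 1.25 to 45/32 = 1.41 times the later one.
- High-dose arm, 48 kg on 150 mg against 55 kg on 300 mg: (150/48)/(300/55) = 3.13/5.45 = 0.57 times.

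These weights are not from the documents; they show only that the sign is open.

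**The case against.** **The eCRF set-up is not visible.** The protocol also speaks of a premature treatment discontinuation visit (3.5, 9.7), which could have its own eCRF label. That is possible. However, 5.6.2 calls the 4-week visit the subject's Week 208 visit, and Table 6-2 assigns it to the EOT column, so the shared label is what the text supports.

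**Completed subjects might mean 208 weeks of treatment completed.** SAP 2.3.1 does tabulate completion of the treatment period separately, and on that reading the mixing would vanish. But the 2020 SAP has the same PK wording and plans full analyses at Weeks 24 and 52 (2.14), when subjects still on schedule could not have completed 208 weeks. The Week 224 definition fits those analyses no better. What stands is that the term is undefined and cannot be relied on to exclude early stoppers.

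**The missed-dose rule may catch some.** Site visits in years 2–4 are 12 or 16 weeks apart, so a stop recognised late could lead to a sample after a missed dose, which the rule would drop. This stands for those subjects, but not for one sampled on time.

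**The impact is limited.** This also stands. The PK tables are descriptive, the Week 104 and 156 rows are not affected by this labelling, treatment completion is tabulated elsewhere, and the listings show sample date and time since first dose. A reader could trace the early samples, but the summary rows would still be mislabelled.

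**Conclusion.** The point holds on the text. Following the plan as written puts early stoppers' EOT and follow-up samples into the Week 208 and Week 224 PK rows. The Week 208 samples are early by weeks to months for stops in the fourth year, and by 3.7 years for a last dose at Week 12. Footnote 3 of Table 14-1 is not true for these subjects. This assumes that the eCRF uses the protocol's visit names and that early stoppers attend as asked.

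Two stronger readings are tempting and are not supported:
- *That the Week 208 mean is overstated by a calculable amount.* The weights and half-life needed are not in the documents, and the bias can go either way once doses change at 25 or 50 kg. The affected Week 208 samples are still about 4-week troughs.
- *That up to 40% of the row is affected.* The 30–40% in SAP 2.5.4 is a cut-off for how far to summarise long-term PASI and IGA data. It counts missing values. It is not a dropout forecast, and it says nothing about discontinuers who attend and give blood.

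The Week 12 efficacy analyses, AUC84-112d, Cmax and Tmax are unaffected. It is a labelling fault in a descriptive secondary endpoint, worth correcting before the final tables.

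**What to change.** In SAP 2.9:
- Limit the Week 208 and Week 224 PK rows, in both summaries, to subjects who received the Week 204 dose.
- Show the EOT and follow-up samples of earlier stoppers in separate *early EOT* and *early follow-up* rows, with time since first dose and time since last dose.
- Do not map off-treatment follow-up samples into on-treatment visit rows by study day.
- State that *completed subjects* does not mean completion of 208 weeks of treatment.

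The cost is a few sentences in the SAP and one row-assignment rule in programming. Actual sample dates and times (Protocol 6.6.3) and the date of last dose (SAP 2.1.1.4) are already collected. The downside is a smaller n in the Week 208 and Week 224 rows.
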